No pharmacological dilation will be used in this study. Subjects will be in a dark room aiming to achieve a natural pupil diameter of at least 5 mm. Upon inclusion, if a subject cannot achieve a non-dilated pupil diameter of at least 5 mm, they will be excluded from the study. If a subject meets a 5 mm pupil on most time points/lenses, but not all, inclusion of data acquired smaller than 5 mm will be scaled to 5 mm and considered on an individual basis.

Equipment:

1. An aberrometer (e.g. COAS-HD or CSO Osiris) will be used for all optical measures. The aberration data will be obtained for central 3- and 5-mm diameter areas. Wavefront data will be reconstructed by both modal (up to 6th order Zernike polynomials) and zonal (local slope) methods.
2. A Medmont corneal topographer will be used following each set of aberration measures to also monitor the tear film upon the eye/contact lens.

SUBJECTSSample Size:

This section describes the rationale and approach used to establish the minimum sample size (N) needed to achieve 80% power at a nominal significance level $\alpha=0.05$ for detecting a mean difference between percentage change in RMS of higher-order wavefront aberrations measured over a 12-hr period for the test lenses and the percentage change observed without a contact lens (no-CL). For each subject and lens, a series of five RMS measurements will be obtained at 0 hours (baseline) and at six, 2-hr intervals within each period. Technically, the statistical power for testing the contact lens main effect will depend not only on the structure of the covariance matrix but also on how the baseline measurements recorded at time=0 hours are incorporated into the statistical model(s). But, given the degree of uncertainty about the input parameter values required to estimate sample size, we believe it reasonable to base initial calculations on a dependent sample t-test on a mean difference score under the assumption of no differential carryover effect. Thus, the target parameter of interest for our primary analysis corresponds to the true difference in the mean post-baseline percentage change over 12 hours between each of the test contact lenses and no-CL for N subjects. Note that this test would be equivalent to testing the interaction of "lens" and "hours of use" factors in a two-way repeated measurements ANOVA.

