Data was not available on the two test lenses, so we used previously published data on an ALCON lens expected to provide similar responses. Specifically, we approximated parameter values for [1] effect size, [2] within-subject variance, and [3] within-subject correlation from the data reported in two previous studies. Specifically, Montes-Mico, *et al* (2013) measured wavefront aberrations in 15 myopic eyes before and at 2-hr intervals after contact lens fitting over a 12-hr period. Using the 5-mm pupil diameter data presented in Figure 2 of the referenced paper, we estimated that the group-averaged percentage change between the baseline (i.e., 2-hr after lens fitting) and the final measurement (i.e., after 12-hr wearing time) of ~3% and ~5% for no-CL and DAILIES TOTAL ONE (DT1) lens, respectively. Note that this difference between no-CL and DT1 was smaller than any of the other lenses under test, but mirrors the expectation for the current test lenses. To allow for mean differences larger than the observed 2% mean difference between each of the test lenses and no-CL in the current study, we added a 1.5% non-inferiority margin; thus, our sample size calculation assumes a 'null difference' of 3.5%.

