where μ is the overall mean, α_i is the effect for the i^{th} sequence, $\rho_{j(i)}$ is the random effect for the j^{th} individual within the i^{th} sequence (i.e. $\rho_{j(i)} \sim N(0, \sigma_\rho^2)$), γ_k is the effect of the k^{th} period, τ_l is the effect of the l^{th} lens effect and λ_m is the effect of the m^{th} carryover effect with e_{ijkl} being the NIID residual term (i.e., $e_{ijkl} \sim N(0, \sigma_e^2)$). Assuming that there is no statistical evidence of a period x lens interaction ($\gamma\tau_{kl}$), we will use a one-sided equivalence (i.e., non-inferiority) test to determine whether the average percentage increase in higher-order RMS induced by Dailies1 Lens is no worse than the average increase without a contact lens. In practice we can use a single directional paired-sample t-test to test the null hypotheses. If we reject H_0 we should conclude that the percentage increase over a 12-hour period in higher-order RMS induced by each of the test lenses is no worse than the increase measured without a contact lens. In this context, smaller differences in the mean difference in higher-order RMS are “better.” Thus, the statistical hypotheses are arranged so that rejecting the null hypothesis for the specified null difference implies that, the observed mean change over 12 hours for each of the test lenses is not significantly worse than the mean change with no-CL. i.e.,

$$H_0: \mu_D - \mu_{NC} \geq M_{IN} \text{ versus } H_a: \mu_D - \mu_{NC} < M_{IN}$$

Interpretation of non-inferiority test of the Dallies Total1 (test) to the reference non-contact lens (active control). Shaded area represents the non-inferiority range. Hypotheses are arranged so that larger mean difference values lead to rejection of the null hypothesis. ■ = observed point estimate of mean difference; both A and C show 1-sided confidence intervals; B and D show 2-sided CIs. Both A and E imply that Dallies Total1 is non-inferior to active non-contact lens control because the entire CI is below non-inferiority margin (3.25%). C and D imply the Dallies is inferior although a larger sample is needed to shrink the CI so that the entire interval C falls in the region of inferiority.

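### The 3.5% non-inferiority limit already contains the expected 2% lens deficit, yet passing it is read as the lens being no worse than no lens

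*Combined protocol and SAP*

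**What the plan says.** The Sample Size section reads two 12-hour changes in higher-order RMS from a published figure: "of ~3% and ~5% for no-CL and DAILIES TOTAL ONE (DT1) lens, respectively". It says the resulting 2-point gap is what is expected of the current test lenses. It then gives the purpose of the next step as "To allow for mean differences larger than the observed 2% mean difference between each of the test lenses and no-CL in the current study". The step itself is an addition to that gap, in these words: "we added a 1.5% non-inferiority margin; thus, our sample size calculation assumes a 'null difference' of 3.5"%. The power target is the N "needed to achieve 80% power at a nominal significance level" of 0.05. Table 1 tests assumed true differences from 2.00 to 3.00 points against the 3.5 null.

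The Statistical Analysis section states: "we will use a one-sided equivalence (i.e., non-inferiority) test", and "In practice we can use a single directional paired-sample t-test to test the null hypotheses". The null is that the lens minus no-lens difference is at least M_IN. The hypothesis line gives M_IN no number, and the figure legend gives the margin as 3.25%. On interpretation, the section begins "rejecting the null hypothesis for the specified null difference implies that, the observed mean change over 12 hours for each of the test lenses is"; its sentence goes on to describe that change as no significant worsening compared with no lens. Hypotheses 1 and 2 in the synopsis say that each lens varies over the day to a degree not significantly different from the naked eye.

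**The concern.** A non-inferiority limit is the largest deficit one is prepared to accept, measured from zero difference. The deficit one expects belongs in the power calculation, as the assumed truth. Here the expected 2 points does both jobs: it is part of the 3.5 limit, and it is the first true difference tested against that limit in Table 1. Under this construction a worse expected lens earns a looser limit. With an expected gap of 4 points, for example, the same step would give 4 + 1.5 = 5.5. The documents offer no optical or clinical reason for either 1.5 or 3.5.

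The conclusion drawn from a pass is at stake. Passing shows that the deficit is below 3.5 points. The plan reads it as the lens being no worse than the naked eye, and the same data could contradict that reading.

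**Working it through.** **Inputs.** N=21 completers (synopsis; Sample Size). SD 2.1% per condition and r = 0.70, 0.75, 0.80 (Sample Size). Limit 3.5 (Sample Size) or 3.25 (Statistical Analysis figure legend). One-sided alpha 0.05. Expected difference 5 − 3 = 2 points.

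**Formulae.** SD of the paired difference = 2.1 × √(2(1 − r)), giving 1.627, 1.485 and 1.328 for r = 0.70, 0.75 and 0.80. Noncentrality δ = √N × (true difference − limit) / SD of difference. Pass probability = P(t with N − 1 df and noncentrality δ falls below the 5% point of t). For N=21 that point is −1.725.

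**The plan's own figures.** With null 3.5, all 15 rows of Table 1(b) reproduce to three decimals. Rows 1 to 3 give 0.810, 0.822 and 0.838. Row 12 (true 2.75, r=0.80, N=21) gives 0.803. The table's arithmetic is correct, and it confirms that 3.5 is the value tested and that the test is one-sided.

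**Pass probability at N=21, planned SD:**

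| True deficit | Limit | r=0.70 | r=0.75 | r=0.80 |
|---|---|---|---|---|
| 0 | 3.5 | >0.999 | >0.999 | >0.999 |
| 2 | 3.5 | 0.993 | 0.998 | 0.9996 |
| 3 | 3.5 | 0.39 | 0.44 | 0.51 |
| 2 | 3.25 | 0.960 | 0.981 | 0.994 |
| 3 | 3.25 | 0.17 | 0.18 | 0.21 |

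For the second row, δ = 4.583 × (2 − 3.5) / 1.627 = −4.23 at r=0.70, and −5.18 at r=0.80.

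**Does a passing trial also show harm?** At the planned SD, an observed mean deficit up to about 2.9 (r=0.70) or 3.0 (r=0.80) still passes the 3.5 limit: 3.5 − 1.725 × 1.627/√21 = 2.89, and 3.5 − 1.725 × 1.328/√21 = 3.00. A deficit is significantly above zero (two-sided 0.05) from 2.086 × 1.627/√21 = 0.74, or 2.086 × 1.328/√21 = 0.60. Every observed deficit between those bounds is both a pass and a significant deficit. Simulating trials at a true 2 points, the two occur together in 99.2% (r=0.70) to 99.96% (r=0.80).

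**Sensitivity to the SD.** The Sample Size section turns a variance of 4.41 × 10⁻⁴ µm² (SD 0.021 µm) into 2.1% without giving a baseline RMS; the two agree only if that RMS is 1 µm. As assumptions, 0.5 µm would give 0.021/0.5 = 4.2% and 0.3 µm would give 0.021/0.3 = 7%. At limit 3.5 and a true 2 points, the pass probability for r = 0.70, 0.75, 0.80 is then 0.65, 0.72, 0.80 (SD 4.2%) or 0.34, 0.38, 0.44 (SD 7%). At SD 4.2%, 42% to 71% of trials both pass and show a significant deficit.

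**The 1.5 points measured from zero.** Only the distance from truth to limit enters δ, so Table 1 carries over with 2 subtracted from each mean difference and from the null. At N=21 and the planned SD:

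| True deficit | Limit | r=0.70 | r=0.75 | r=0.80 |
|---|---|---|---|---|
| 0 | 1.5 | 0.993 | 0.998 | 0.9996 |
| 0.75 | 1.5 | 0.65 | 0.72 | 0.80 |
| 2 | 1.5 | 0.0013 | 0.0009 | 0.0005 |

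At an assumed SD of 4.2%, power at zero difference is 0.65, 0.72, 0.80.

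**The case against.** The strongest reply is that 99% is ordinary power. Any non-inferiority test passes a true value well inside its limit, and being significantly worse than zero while inside the limit is a recognised, permitted outcome. This stands. A reader might infer from the figures that the test has a 99% false-positive rate against a nominal 5%. It does not: that comparison scores the test against a limit of 1.5 from zero, which the plan does not test. At its own limit the error rate is 5%.

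A reader might also infer that the rule cannot tell lenses apart. That is too strong: the pass rate falls to 0.39 to 0.51 at a true 3 points. At an assumed SD of 7%, a lens with no deficit passes 0.89 to 0.97 of the time, against 0.34 to 0.44 for one 2 points worse. A pass does carry information, namely an upper bound on the deficit.

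Third, both 3.5 and 3.25 exceed the naked eye's change of about 3%, which invites the inference that the limit is too wide for that reason alone. The documents do not support a ceiling of that kind. The 3% was read from a figure covering 2 to 12 hours in 15 eyes, whereas the endpoint runs from 0 to 12 hours, and nothing in the plan requires the limit to lie below the reference's own change.

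Finally, 1.5 has no more justification in the documents than 3.5. This too stands, and it limits the fix to requiring a limit defined and justified from zero. What the reply does not answer is that the limit was built from the expected deficit while a pass is read as no deficit.

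**Conclusion.** The point holds as a fault in how the limit is built and read. The expected 2-point deficit is absorbed into the 3.5 limit, and a pass is then reported as no worse than, or not significantly worse than, no lens. If the lenses behave as the plan expects, following the plan at its own inputs gives that conclusion 99.3% to 99.96% of the time (96.0% to 99.4% at 3.25), and at 3.5 at least 99% of the trials would themselves show a significant deficit. These sizes rest on N=21, SD 2.1% and r of 0.70 to 0.80. The SD is the weakest input, and larger values bring the pass rate down to 65% to 80% (assumed SD 4.2%) or 34% to 44% (assumed SD 7%). The construction of the limit and the over-reading of a pass do not depend on the SD. The coexistence of 3.5 and 3.25 is a separate inconsistency, and choosing between them would not cure this one.

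**What to change.** Define M_IN as an acceptable deficit measured from zero, give the reason for its size, and use the assumed true difference only in the power calculation. State one value in the Sample Size text, Table 1 and the Statistical Analysis section, including the figure legend, so that 3.5% and 3.25% are reconciled.

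The plan's own named margin, 1.5 points, is the natural candidate. With it, N=21 can stay, and the power statement should carry its dependence on r: 0.993 to 0.9996 at zero difference, and 0.65, 0.72 and 0.80 at a true 0.75 points for r = 0.70, 0.75 and 0.80. The 0.75 is only row 12 of Table 1 shifted by 2, not an expectation found in the documents, and it should not be presented as 80% power across the range of r. The text should also say that a lens 2 points worse would pass about 0.1% of the time.

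If the sponsor keeps a larger limit, confine the conclusion to the lens being less than that many points worse than no lens. Report the confidence interval against zero beside it, and drop the readings of no worse than and not significantly different.

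The cost is wording and a relabelled table, with no added subjects or visits. The real price is that, at 1.5, a lens performing as the plan expects would fail, and no increase in N changes that. Power at zero difference would also fall to 0.65 to 0.80 if the SD were 4.2%.

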Our within-subject variability and correlation estimates were taken from Cheng, *et al* (2004) who reported on the stability of clinical monochromatic aberrometry measurements over a wide range of time scales. First, temporal variability of wavefront root mean square (RMS) error, excluding defocus and astigmatism, was tracked across five repeated measurements for 4 subjects at four different time scales. The averaged variance estimates for different time scales ranged from $8.10 \times 10^{-5} \mu\text{m}^2$ ($t < 1$ second) to $9.73 \times 10^{-4} \mu\text{m}^2$ ($t < 1$ year). For our calculations, we used their reported value of $4.41 \times 10^{-4} \mu\text{m}^2$ ($t < 1$ week) as our variance estimate, which translates to a standard deviation of 2.1%. We expect that this is a worst-case scenario because the value was derived by calculating the between-day variances for individual trials across five days for each subject and then calculating the average across the four subjects and five trials on each day. Our data will be multiple measurements taken within a 12-hr period on the same day. Second, Cheng, *et al* (2004) reported a within-subject correlation estimate of $r=0.799$ that was based on a linear regression analysis of the higher-order RMS error measurements over a one-year time scale for subject AB. Again, because the time-scale in the current study proposal is only 12 hours (i.e., is much shorter than 1 year), we expect that the magnitude of the within-subject correlation in our sample is likely to be 0.80 higher. For purposes of the sample size calculation, we used three values for the correlation parameter, i.e., $r = \{0.70, 0.75, \text{ and } 0.80\}$. The input parameters for this sample size calculation scenario are shown in Table 1(a). The actual power and number of paired observations for this scenario are presented in Table 1(b) and were obtained using SAS 9.4 by varying both the mean difference and the correlation parameters.

Table 1 (a)

Fixed Scenario	
Distribution	Normal
Method	Exact
Number of Null	L
Alpha	3.50 %
Standard	0.05
Nominal	2.10 %
	0.80

Table 1 (b)

Index	Mean Diff	Corr	Actual Power	N Pairs
1	2.00	0.70	0.810	9
2		0.75	0.822	8
3		0.80	0.838	7
4	2.25	0.70	0.802	12
5		0.75	0.829	11
6		0.80	0.824	9
7	2.50	0.70	0.804	18
8		0.75	0.822	16
9		0.80	0.819	13
10	2.75	0.70	0.806	31
11		0.75	0.805	26
12		0.80	0.803	21
13	3.00	0.70	0.801	67
14		0.75	0.801	56
15		0.80	0.808	46

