The primary outcome measure in this study will be a derived variable indexing the percentage change in the RMS of higher-order wavefront aberrations (microns) at a 3 and 5 mm pupil from baseline to 12 hours. For each participant, we will convert the data from microns into the percentage change in RMS, $\% \Delta_{i(12-0)k} = 100 \times (\text{RMS}_{i12k} - \text{RMS}_{i0k}) / \text{RMS}_{i0k}$ where $i=1,2,\dots,N$ participant, j represents time (hrs) $\in (0 \text{ (BL)}, 2, \dots, 12)$, and k denotes lens. Our initial analysis will compare the mean $\% \Delta_{(12-0)\text{test}}$ computed across N participants for each of the Air Optix plus Hydraglyde and Air Optix Aqua lenses independently with the mean $\% \Delta_{(12-0)\text{NCL}}$ with no contact lens.

Secondary:

1. *Subject-reported vision-stability (0-100 scale, while viewing at distance)*
2. *Root Mean Square Fit Error.* For each optical measurement, the wavefront will be reconstructed using both a 'typical' modal (Zernike) reconstruction and zonal (local integration) reconstruction. The difference between these two reconstructed wavefronts will be evaluated.

TESTING PROCEDURES:

In office testing will be done at study entry, and following 2 ± 1 days of lens wear for each of the follow up visits.

Testing Day 1, Visit 1 Baseline/Inclusion:

1. Demographics
2. Ocular history
3. Entrance Snellen visual acuity
4. Entrance ocular health (with conjunctival and corneal staining)
5. Habitual lens information (type, power)
6. Habitual lens use (wearing schedule, replacement schedule, hours per day, insertion time, removal time)
7. Subjective refraction (best objective with an additional -0.25 D for subjective improvement)
8. Fit evaluation of all lens pairs. If all lens pairs do not fit adequately enough per investigator clinical determination for dispensing, subject will be exited from the study.
9. Snellen acuity of each eye for all lens pairs.

Testing Day 2, Visit 1-7 Naked eye diurnal measures:

1. Subjects will first have aberrometry, Medmont topography, and subjective quality measurements acquired every 2 ± 0.5 hours for 12 ± 1 hours without any lenses (no lens, baseline). The subject will wear their habitual spectacles between measurement periods.

Testing Day 3, Visit 1-7 and Testing Day 4, Visit 1-7 (each separated by a day of washout and 2 ± 1 days of study lens wear):

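### The planning SD of 2.1% is 0.021 microns relabelled as a percentage, so the 80% power stated for N=21 is not supported

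*Combined protocol and SAP*

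**What the plan says.** The Sample Size section sets out to "establish the minimum sample size (N) needed to achieve 80% power" at alpha 0.05, using a paired t-test on the difference in percentage change between each test lens and no lens.

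- **Effect.** From published 5 mm data, the 12-hour change is put at about 3% without a lens and 5% with a comparable lens. The resulting difference of 2% is said to be one that "mirrors the expectation for the current test lenses". Adding 1.5%, "our sample size calculation assumes a 'null difference' of 3.5" percent.
- **Variability.** From a second published study, the plan uses 4.41e-4 square microns (time scale under one week) "as our variance estimate, which translates to a standard deviation of 2.1" percent. It adds: "We expect that this is a worst-case scenario". The reason given is that the source variance is between days, whereas the trial measures within one day.
- **Table 1.** The SD enters Table 1(a) as 2.10%. Table 1(b) varies the true difference (2.00 to 3.00) and the correlation (0.70 to 0.80) and holds the SD fixed. The target is 21 completers, with 24 enrolled.
- **Endpoint.** Under Outcome Measures, Primary, "we will convert the data from microns into the percentage change in RMS", that is 100 x (RMS12 - RMS0)/RMS0, "at a 3 and 5 mm pupil from baseline to 12 hours".

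**The concern.** A variance in square microns has an SD in microns. To express that SD as a percentage of baseline it must be divided by a baseline RMS. The plan shows no such division and gives no baseline or mean higher-order RMS at either pupil diameter. The figure of 2.1 is 0.021 x 100, which is a percentage of baseline only at a baseline of exactly 1 micron.

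The numerator of the power calculation (3.5 minus the true difference) is in percent of baseline. The denominator is not, unless that unstated baseline applies. Every row of Table 1(b) uses this SD. If baseline RMS is below 1 micron, the percentage SD is larger than planned and power is lower. The risk is an inconclusive trial: a lens truly within the margin may fail to show it. The false-positive rate is not affected, because the t-test uses the observed SD.

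A second gap concerns the same input. The source variance describes RMS readings, whereas the endpoint is a 12-hour change. The plan does not say how one becomes the other.

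**Working it through.** **Inputs from the Sample Size section:** null difference 3.5; true difference 2.00 to 3.00; correlation r = 0.70 to 0.80; source variance 4.41e-4 square microns; N = 21. One-sided alpha 0.05 follows from the directional test under Statistical Analysis. **Not in the documents:** baseline RMS, here an assumed range of 0.1 to 1.0 micron, with the absolute SD held at 0.021 microns throughout.

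**Formulas (as in the plan):** SD of the paired difference = SD x sqrt(2(1 - r)). Noncentrality, taken as distance below the null, = sqrt(N) x (3.5 - true difference) / SD of the paired difference. Power comes from the noncentral t with N - 1 degrees of freedom.

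**Step 1: reproduce the plan.** With SD 2.1 and r = 0.80, the SD of the difference is 2.1 x sqrt(0.4) = 1.328. For a true difference of 2.75 and N = 21, noncentrality is sqrt(21) x 0.75/1.328 = 2.588 and power is 0.803, as printed. All 15 rows reproduce in both N and power. A two-sided 0.05 test would need 27 pairs in this row, so the table is one-sided.

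**Step 2: check the units.** sqrt(4.41e-4) = 0.0210 microns. As a percentage of baseline it is 100 x 0.021/RMS0, which equals 2.1% only when RMS0 = 1.0 micron.

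**Step 3: power at N = 21, r = 0.80, with the SD rescaled.**

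| Assumed RMS0 (microns) | SD (%) | Power, diff 2.75 | Power, diff 2.0 | Power, diff 0 | Pairs for 80%, diff 2.0 |
|---|---|---|---|---|---|
| 1.0 | 2.1 | 0.80 | >0.99 | >0.99 | 7 |
| 0.75 | 2.8 | 0.59 | 0.98 | >0.99 | 11 |
| 0.5 | 4.2 | 0.35 | 0.80 | >0.99 | 21 |
| 0.3 | 7.0 | 0.19 | 0.44 | 0.97 | 56 |
| 0.2 | 10.5 | 0.13 | 0.26 | 0.75 | 123 |
| 0.1 | 21.0 | 0.08 | 0.13 | 0.32 | 487 |

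**Step 4: invert.** N = 21 gives 80% power only if baseline RMS is at least about 0.995 micron (difference 2.75), 0.50 (2.0), 0.30 (1.0) or 0.21 (0). Equivalently, the largest true difference with 80% power is 2.75 at 1.0 micron, 2.0 at 0.5, 1.0 at 0.3 and -0.2 at 0.2.

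**Step 5: favourable variance.** The smallest variance the plan quotes is 8.10e-5 (SD 0.009 microns). This is close to 0.021/sqrt(5) = 0.0094, the SD if five repeats with independent errors were averaged. With SD 0.009, power at 2.75 is 0.90 at 0.5 micron, 0.54 at 0.3 and 0.32 at 0.2. At 2.0 it is 0.97 at 0.3, 0.75 at 0.2 and 0.32 at 0.1.

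**Step 6: reading versus change (illustration, 1 micron, difference 2.75).** If the two readings within a day have independent errors, the SD of a change is 2.1 x sqrt(2) = 2.97. Keeping r = 0.80 between conditions, power is 0.55 (0.97 at a difference of 2.0). If all four readings are independent, the SD of the difference is 4.2 and power is 0.20.

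**The case against.** The unit error itself has no answer in the text: no baseline RMS, redaction or damaged table repairs it. The strongest case is that the consequence may be small.

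- **Expected effect.** The plan expects a difference near 2.0, where Table 1(b) needs only 7 to 9 pairs. N = 21 then tolerates a doubled SD at r = 0.80. This stands, but the slack ends at a baseline of about 0.50 micron. The plan never says which row supplied N = 21; that it was the 2.75 row is inferred, because 21 appears nowhere else in the table.
- **Conservative variance and correlation.** The source variance is between days, r may exceed 0.80, and "a series of five RMS measurements will be obtained at 0 hours (baseline") may mean averaged repeats. With r = 0.90 (not a value the plan uses), power at 2.75 is 0.84 at 0.75 micron. Adding five averaged repeats gives 0.99 at 0.5 and 0.77 at 0.3. So adequate power is possible. But the worst-case remark concerns time scale rather than units, and the plan does not make this argument.
- **Fixed absolute SD.** The low-baseline figures hold 0.021 microns constant as RMS falls, and the pupil diameter behind the source variance is not given. This stands as a limit on the size of the loss. It also counts against simply dividing 0.021 by a baseline at each pupil.
- **Admitted uncertainty.** The plan calls these initial calculations with uncertain inputs. That is a reason to vary the SD, the one uncertain input the table holds fixed.

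**Conclusion.** The concern holds. The 2.1% is an SD in microns multiplied by 100, and Table 1(b) sets it against a margin in percent of baseline. With the plan's SD of 0.021 microns and r = 0.80, the 80% in the N = 21 row requires a baseline RMS of about 1 micron. At 0.5 micron it falls to 0.35 and at 0.3 to 0.19.

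The true loss cannot be fixed from the documents. It depends on the baseline RMS, the true difference, the correlation and whether repeats are averaged. At a difference of 2.0, power is still 0.80 at 0.5 micron. A lens identical to no lens would still pass with probability 0.75 at 0.2 micron. The stated power is therefore unsupported, and the trial is not shown to be underpowered in every case. The change-score gap is separate and could lower power further. The sample size statement must be corrected before it is relied on.

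**What to change.** 1. Replace 2.1% with an SD of the 12-hour percentage change. Taking it directly from change-score data is safer. The alternative is 100 x 0.021/RMS0 carried to a change score, with the correlation between the 0-hour and 12-hour readings stated; this also requires the pupil diameter to which the source variance applies.
2. State the expected baseline higher-order RMS at 3 mm and at 5 mm, with sources.
3. Say whether five repeats per time point are averaged.
4. Rerun Table 1(b) over a range of SDs. Then restate the power N = 21 delivers, or the largest true difference at which it gives 80% power against 3.5%.

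The cost is one rerun of the calculation and a reworded paragraph. The stated power may become less favourable, and N = 21 may prove to support only a true difference smaller than 2.75. Whether N must change depends on the rerun.

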Note that the paired-sample t test assumes normally distributed data and requires $N \geq 2$. The test statistics are

$$t = N^{1/2} \left(\frac{\bar{d} - \mu_0}{s_d} \right) \sim t(N - 1, \delta) \text{ or, equivalently, } t^2 \sim F(1, N - 1, \delta^2)$$

where \bar{d} and s_d are the sample mean and standard deviation of the differences, and

$$\delta = N^{1/2} \left(\frac{\mu_{diff} - \mu_0}{\sigma_{diff}} \right) \text{ and } \sigma_{diff} = (\sigma_1^2 + \sigma_2^2 - 2\rho\sigma_1\sigma_2)^{1/2}$$

represent the non-centrality parameter and standard deviation of the paired difference scores, respectively. In order to compensate for potential data loss due to subject attrition, we propose increasing the targeted sample size of $N=21$ to 24 which is based on a post-consent/randomization attrition rate between 5 and 10% observed in 50+ studies in our laboratory that have required multiple (>1) daytime visits.

Inclusion Criteria:

1. Habitual prescription +5.00 D to -6.00 D
2. 18-35 years of age
3. No history of issues of eye alignment or binocularity by self-report
4. No doctor diagnosed, self-reported accommodative or binocular vision issues
5. No doctor diagnosed, self-reported ocular surface disease or dry eye requiring regular, ongoing treatment
6. The subject must appear able and willing to adhere to the instructions set forth in this clinical protocol.
7. Vertex corrected refractive cylinder must be -0.75 or less.
8. Visual acuity best correctable to 20/25 or better for each eye
9. The subject must read and sign the Informed Consent form.
10. No active conditions that may prevent soft contact lens wear.
11. Mesopic pupil size >5.00 mm.

LENSES

Lens powers are based on vertexed (15 mm) spherical equivalent refraction (performed upon study entry) and matched between all lens types.

1. Baseline no lens
 2. Air Optix plus Hydraglyde on daily disposable basis
 3. Air Optix Aqua on daily disposable basis
- (*ALCON supplies all lenses)

OUTCOME MEASURESPrimary:

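### The sample size puts a between-day SD of RMS level and a one-subject, one-year correlation into a formula for paired 12-hour changes, so 80% power at N=21 is unsupported.

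*Combined protocol and SAP*

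**What the plan says.** Under SUBJECTS, Sample Size, the protocol aims for 80% power at alpha 0.05 to compare 12-hour percentage change in higher-order RMS between each test lens and no lens. The calculation is a paired t-test with a null difference of 3.5%. The formulas after Table 1 use δ and σ_diff, which "represent the non-centrality parameter and standard deviation of the paired difference scores". Under OUTCOME MEASURES, Primary, the score is each participant's percentage change from 0 to 12 hours.

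The protocol had no data on the two test lenses. From two published studies, it says, "we approximated parameter values for [1] effect size, [2] within-subject variance, and [3] within-subject correlation". In detail:

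- **Mean difference.** About 2%, from a related lens. The plan says this "mirrors the expectation for the current test lenses".
- **SD.** 2.1%, from a variance of 4.41 × 10⁻⁴ μm² on a time scale of under one week. It came from "calculating the between-day variances for individual trials across five days for each subject and then calculating the average across the four subjects" and the five trials on each day. The plan calls it a worst case.
- **Correlation.** 0.799, "based on a linear regression analysis of the higher-order RMS error measurements over a one-year time scale" in a single subject. The plan expects 0.80 or more "because the time-scale in the current study proposal is only 12 hours", and tabulates 0.70, 0.75 and 0.80.

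Table 1(b) was produced "by varying both the mean difference and the correlation parameters"; the SD stays at 2.1%. The plan bases its calculation on a simple paired t-test "given the degree of uncertainty about the input parameter values required to estimate sample size". The target is 21 completers, with up to 24 enrolled.

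**The concern.** σ_diff needs two things: the SD across subjects of the 12-hour percentage change in each condition, and the correlation of those changes between the lens day and the no-lens day. The plan supplies neither.

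- **The 2.1% describes a level, not a change.** A change uses two readings, so its SD can exceed that of one reading, by √2 if the errors are independent. A within-subject variance also leaves out real differences between subjects in how much they change over the day.
- **The 0.799 comes from one person's RMS levels over a year.** One subject cannot show how changes on two days correlate across subjects, and the documents do not settle what r is meant to measure. If 2.1% already excludes stable between-subject variation, reducing it again through r is not justified. If r is the same-day correlation of the 0-hour and 12-hour readings, it belongs inside the SD of each change and not between conditions.

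The argument that 12 hours is shorter than a week or a year concerns readings within one day. The test compares changes made on different testing days.

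The primary test is for non-inferiority, so a failure to reject could reflect low power and not the lens. The plan gives no SD limit against which to check this.

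**Working it through.** **Inputs.** From the Sample Size section: null difference 3.5%, SD 2.1%, r = 0.70, 0.75 or 0.80, alpha 0.05. The one-sided paired t-test is from STATISTICAL ANALYSIS. 2.1% is taken at face value.

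**Formulas.** σ_diff = SD × √(2(1 − r)) for equal SDs. δ = √N × (3.5 − mean difference) / σ_diff in absolute value. Power comes from the noncentral t with N − 1 degrees of freedom.

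**The plan's own figures.** All 15 rows of Table 1(b) reproduce with a one-sided test. For the only row with N=21 (difference 2.75%, r=0.80): σ_diff = 2.1 × √0.40 = 1.328; δ = √21 × 0.75 / 1.328 = 2.59; power 0.803. A two-sided test would need 27 pairs.

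**Other readings of the same 2.1%.**

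- SD of one reading, with r the same-day correlation. Each change has SD 2.1 × √(2(1 − r)). With changes uncorrelated between days, σ_diff = 2.1 × √(4(1 − r)): 1.878 at r=0.80 and 2.300 at r=0.70.
- SD of a change, uncorrelated between conditions: 2.1 × √2 = 2.970.
- SD of one reading, no correlation anywhere: 2.1 × √4 = 4.200.

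**Power of 21 pairs at each mean difference.**

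| Reading of 2.1% and r | σ_diff | 2.00% | 2.25% | 2.50% | 2.75% | Largest difference keeping 80% |
|---|---|---|---|---|---|---|
| Plan, r=0.80 | 1.33 | >99% | 99% | 95% | 80% | 2.75% |
| Plan, r=0.70 | 1.63 | 99% | 96% | 86% | 65% | 2.59% |
| One reading, same-day r=0.80 | 1.88 | 97% | 90% | 76% | 55% | 2.44% |
| One reading, same-day r=0.70 | 2.30 | 89% | 78% | 61% | 42% | 2.21% |
| Change score, no correlation | 2.97 | 72% | 59% | 44% | 30% | 1.83% |
| One reading, no correlation | 4.20 | 47% | 37% | 28% | 20% | 1.14% |

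The plan's r=0.75 (σ_diff 1.485) gives 72% at 2.75%.

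**Largest σ_diff that keeps 80%.** These limits do not depend on how 2.1% or r is read.

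| Completers | 2.00% | 2.25% | 2.50% | 2.75% |
|---|---|---|---|---|
| 21 | 2.67 | 2.22 | 1.78 | 1.33 |
| 24 | 2.87 | 2.39 | 1.91 | 1.43 |

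At 2.75% with 21 completers the limit is 1.335 to three decimals, against the plan's 1.328.

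**A case in the plan's favour.** Take same-day r=0.80 and assume that changes correlate 0.5 between days. Then σ_diff = 1.878 × √(1 − 0.5) = 1.328, and power at 2.75% is again 80%.

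**The case against.** The strongest reply is that 21 pairs leave room. The plan expects a difference of about 2%, where Table 1(b) asks for only 7 to 9 pairs. At 2%, four of the six readings above give 89% or more. Considering larger differences is how the plan allows for uncertainty, and its table already shows that 2.75% needs 26 pairs at r=0.75 and 31 at r=0.70. No sentence ties N=21 to the 2.75% row; that link is inferred. All of this stands. It is why the power is called unsupported and not too low.

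The adverse readings are also constructions. A day-level component shared by the 0-hour and 12-hour readings cancels in a change, so the 4.20% case is likely severe. Averaging repeated readings might lower the SD, although the plan does not say it will average. This too is fair. But it shows that the true SD is unknown, and gives no reason to rely on 1.33%.

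Finally, the fault lies in the inputs and not in the table's calculation, and the plan admits that its inputs are uncertain. Yet the table holds fixed the input in doubt here, the SD. Nor is 2.1% itself secure: an SD of 0.021 μm is 2.1% only if mean RMS is 1 μm, and the documents give no mean RMS. If it were 0.5 μm (an assumption), the SD would be 4.2%, and at r=0.80 the power of 21 pairs would be 80% at a 2% difference and 35% at 2.75%. That is a further weakness, on which the finding does not depend.

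**Conclusion.** The concern holds. The SD and correlation entered are not those the formula requires, and the shorter time scale does not make them so. The 80% is unsupported, not disproved: at 2.75%, power for 21 pairs runs from 20% to 80% over the readings tabulated, and at 2% from 47% to above 99%. The documents do not show whether the true paired-difference SD lies below the limits of 2.67% (at a 2% difference) and 1.33% (at 2.75%). These figures assume a one-sided 0.05 test, a 3.5% null difference and 21 complete pairs. The power ranges also take 2.1% at face value; the SD limits do not.

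**What to change.** 1. Replace the single 80% with the power of N=21 over a stated range of paired-difference SDs and mean differences, so that Table 1(b) varies the SD as well as r.
2. Say which mean difference N=21 rests on, and whether r refers to same-day readings or to changes across conditions.
3. Print the largest paired-difference SD that keeps 80% with 21 completers (2.67, 2.22, 1.78 and 1.33% at differences of 2.00, 2.25, 2.50 and 2.75%), so that the observed SD can be checked against it.
4. If one can be obtained, use a directly estimated SD of paired differences in 12-hour percentage change. This is optional, because the plan says that data on the test lenses were not available.

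The cost is a table rerun, revised wording and a less favourable stated power. No subjects are added.
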